7.1.3.2 Human exposure

As with most live attenuated vaccines, CYD-TDV is contraindicated in pregnancy because of a theoretical risk to the fetus. Consequently, no clinical studies have been performed to specifically evaluate the safety of CYD-TDV pregnancy exposure. Indeed, pregnancy has been a strict exclusion criterion in all clinical trials and a negative urine test was required for study inclusion and before each subsequent vaccination. Despite these precautions, a small number of female trial participants were inadvertently exposed during pregnancy; this is not entirely surprising given that, on average, at least 50% of pregnancies are unplanned.⁵ Given this, data from 19 clinical trials were recently pooled to evaluate pregnancy and birth outcomes among trial women inadvertently exposed to CYD-TDV during pregnancy.⁶ A total of 615 trial participants across 19 trials became pregnant during trial follow-up, 404 of whom had received CYD-TDV and 211 placebo (given the 2:1 randomization). For the pregnancy exposure safety analysis, the pregnancy was considered “exposed” if vaccination occurred during pregnancy or up to 30 days preceding the LMP if the LMP was known, or 44 days before the estimated conception date (ECD) if LMP was unavailable, where ECD was based on gestational age at ultrasound examination. Of the 404 pregnant women who received CYD-TDV during trial follow-up, 58 (14.4%) were classified as “exposed during pregnancy,” whereas 30 (14.2%) of 211 in the placebo group were considered “exposed during pregnancy”. Exposure to CYD-TDV occurred within a few weeks of LMP in most cases, and within approximately a month following LMP in all cases. The proportion of healthy live births was high and relatively balanced between the two groups (81% and 83% for CYD-TDV and placebo exposed pregnancies, respectively). In addition, 10.3% of CYD-TDV exposed pregnancies resulted in the loss of the fetus, compared with 13.3% of placebo exposed pregnancies. This analysis found no evidence of increased adverse pregnancy or birth outcomes among a small group of clinical trial participants inadvertent exposed to CYD-TDV within a few weeks of conception. While these results are reassuring, this analysis also has notable limitations. First, the sample size was too small to detect an increased risk for most adverse pregnancy outcomes of interest. Second, it is not known whether pregnant women inadvertently exposed to CYD-TDV were comparable to those exposed to placebo as the analysis was conducted in a subset of the randomized population and a comparison of baseline characteristics of the two subgroups was not provided. Finally, the results represent the impact of pregnancy exposure within a few weeks of conception among predominantly adolescents. As such, these results may not be generalizable to pregnancy exposures in a real-world setting, particularly in the context of mass vaccination campaigns.

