9.2.3 Selection of a comparison group

This pregnancy registry study will be a combination of a retrospective (outcomes occurred before the start of participant enrollment) and prospective (outcomes occurred after the start of participant enrollment) cohort study using active identification and enrollment of pregnant women and their offsprings inadvertently exposed to CYD-TDV during pregnancy or up to 30 days preceding the LMP. For reasons described in section 9.1.2, active enrollment of a valid internal comparison group of unexposed pregnant women and their offsprings is not feasible. As such, rates of study AESIs observed among women enrolled in the pregnancy registry and their offsprings will be compared with available background event rates prior to the availability of CYD-TDV for the Brazilian population of similarly aged women and offsprings (i.e., external unexposed comparators) to identify potential safety signals warranting further investigation. Background rates from existing databases (e.g., SISPRENATAL, SINASC, SIM) and other appropriate data sources (e.g., literature) will be used.

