9.2.5 Eligibility criteria

9.2.5.1 Inclusion criteria

- CYD-TDV exposed pregnant women of any age residing in the 30 municipalities of Paraná where public vaccination campaigns have been offered at the time of their pregnancy exposure, and whose pregnancy exposure was reported to Brazil's AEFI PV database (SI-PNI AEPV);
- Valid contact information (in SI-PNI AEPV);
- Study participants must provide a signed and dated informed consent form (ICF) or assent form (AF) (based on local regulations), and/or a signed and dated ICF by the parent(s) or other legally acceptable representative (and by an independent witness if required by local regulations) if a minor.*

* Women who meet the inclusion criteria and provide informed consent to participate and complete the structured interview, but who do not consent to medical record review and/or database linkages will still be included in the study; however, their data will be analyzed separately in a sensitivity analysis.

9.2.5.2 **Exclusion criteria**

- Presence of a major language barrier, medical or psychiatric condition that would prevent a woman from providing informed consent or accurate medical or medication/vaccination histories.

9.2.6 **Investigator selection**

The study investigators were selected on the basis of their expertise in pediatrics, maternal and child health, epidemiology and clinical research, as well as their expertise with Brazil's public and health databases and their access to these databases (Appendix 1). In addition, these investigators were recommended by Paraná's Secretary of Health.

9.3 **VARIABLES**

9.3.1 **Primary endpoints**

The primary study endpoints will include all serious and non-serious maternal, pregnancy related, birth outcomes, neonatal and infant events as described below occurring anytime between cohort entry and the end of follow-up for each event. Although formal diagnostic criteria such as those of the Brighton Collaboration are available for a number of the outcomes of special interest, it is unlikely that these are used in routine clinical practice. As such, the diagnoses will be based on clinician assessment as recorded in the medical record and/or databases.

- **Maternal adverse events following immunization:** will be defined as all reported adverse events following immunization (serious and non-serious) occurring *independent of the pregnancy* (e.g., injection site reactions, systemic reactions).

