9.5 SAMPLE SIZE

Ultimately, the sample size will depend on the number of pregnant women who were inadvertently exposed to CYD-TDV during Paraná's public vaccination campaigns, had this exposure reported to the SI-PNI AEPV database during the study's enrollment period, and provide signed informed consent. As such, every effort will be made to recruit all eligible women. As of 19 December 2018, 214 reports of inadvertent pregnancy exposures had been submitted to the SI-PNI-AEPV reporting system. However, this number could increase if additional vaccinations campaigns are offered during the study enrollment period.

Based on published estimate, adverse pregnancy outcomes such as spontaneous abortions are expected to occur at a frequency of 1/7 (14.3%), low birth weight at 1/12 (8.3%), fetal death/stillbirth at 1/200 (0.5%).⁸ Birth defects occur in 1/135 (0.007) pregnancies for genital and urinary tract defects.⁹ In Brazil, microencephaly occurs at a frequency ranging from 0.0 to 20.32 per 10,000 live births, depending on

the region.¹⁰ Ultimately, the level of precision (expressed as 95% CI) for the observed point estimates will depend on the number of identified women exposed during pregnancy who consent to participate in the pregnancy registry:

Participation rate	Expected number of exposed pregnancies	Expected observed rate (%)	Number of outcomes	Expected 95% CI
100%	214	14.486%	31	(10.06; 19.93)
		8.411	18	(5.06; 12.97)
		0.467	1	(0.01; 2.58)
75%	160	14.375	23	(9.34; 20.78)
		8.125	13	(4.4; 13.49)
		0.625	1	(0.02; 3.42)
50%	107	14.019	15	(8.06; 22.07)
		8.411	9	(3.92; 15.37)
		0.935	1	(0.02; 5.1)

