Serious and severe are not synonymous. The term severe is often used to describe the intensity of a specific event. This is not the same as serious which is based on patient / event outcome or action criteria usually associated with events that pose a threat to a patient's life or functioning. Seriousness, not severity, serves as a guide for defining regulatory reporting obligations.¹³

Medical and scientific judgment will be exercised in deciding whether expedited reporting is appropriate in situations other than those described above, such as important medical events that may not be immediately life-threatening or result in death or hospitalization but may jeopardize the participant or may require intervention to prevent one of the outcomes listed in the definition above.

The pregnancy registry will actively collect AEs specific to the pregnancy, birth, neonatal and infant outcomes of interest, in addition to any maternal AEFI. Pregnancy itself is not considered as an AE, but any complications experience during pregnancy will be considered as AEs, and in some cases could be considered SAEs. The following AEs are always considered SAEs: major congenital malformation, low birth weight, pre-eclampsia, eclampsia, gestational diabetes, preterm delivery, fetal death/stillbirth, death in utero, spontaneous abortion/miscarriage, ectopic pregnancy, elective abortion for medical reason, termination of pregnancy for fetal anomaly (TOPFA), hospitalized dengue, motor-developmental anomalies, and maternal death.

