APPENDIX 2. PREGNANCY RELATED ADVERSE EVENTS OF SPECIAL INTEREST

Outcome	Description
Pregnancy outcomes	
Ectopic pregnancy	
 • Pregnancy with fertilized egg implanted and maturing outside the uterus; • Based on clinician assessment as recorded in the medical record or databases
Pregnancy loss	
Spontaneous abortion/miscarriage	
 • Fetal death with expulsion at <20 weeks of gestation or at weight <500 g if gestational age is unknown; occurred naturally (without outside interference); • Based on clinician assessment as recorded in the medical record or databases
Abortion, unspecified	
 • Premature expulsion of the embryo or a non-viable fetus where the type of abortion (spontaneous or elective) is not mentioned; • Based on clinician assessment as recorded in the medical record or databases
Abortion, medically indicated	
 • Abortion brought on intentionally; includes therapeutic abortion when pregnancy is a threat to the mother's life and/or is the result of sexual assault; • Based on clinician assessment as recorded in the medical record or databases
Termination of pregnancy for fetal anomaly (TOPFA)	
 • Abortion brought on intentionally when the embryo/fetus presents an abnormality
Stillbirth/fetal death	
 • Delivery of a dead fetus at ≥20 weeks of gestation or in fetus weighing >500 grams if gestational age is unknown; • Based on clinician assessment as recorded in the medical record or databases
Death in utero	
 • Fetal death without expulsion at < 20 weeks of gestation; • Based on clinician assessment as recorded in the medical record or databases
Complications of pregnancy	
Hypertensive disorders	All with onset at ≥20 weeks gestation
Gestational hypertension	
 • Hypertension (sustained blood pressure ≥140/90 mmHg) that develops during pregnancy in previously normotensive woman; • Based on clinician assessment as recorded in the medical record or databases
Preeclampsia	
 • Gestational hypertension with proteinuria (>300mg in 24 hrs); • Based on clinician assessment as recorded in the medical record or databases

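### Natural fetal loss before 20 weeks is split by expulsion with no combined outcome, so the spontaneous abortion rate may not match the background rate it is compared with

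*Protocol*

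**What the plan says.** Under the heading Pregnancy loss, Appendix 2 lists several separate outcomes of special interest. Three concern early loss:

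- Spontaneous abortion/miscarriage, defined as: "Fetal death with expulsion at <20 weeks of gestation or at weight <500 g if gestational age is unknown; occurred naturally (without outside interference").
- Death in utero: "Fetal death without expulsion at < 20 weeks of gestation".
- Abortion, unspecified: premature expulsion "where the type of abortion (spontaneous or elective) is not mentioned".

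The same heading also covers medically indicated abortion, termination for fetal anomaly, and stillbirth. Stillbirth is defined by delivery of a dead fetus at 20 weeks or later, with a weight criterion if gestational age is unknown. Section 11.1.1 keeps the split, listing "death in utero, spontaneous abortion/miscarriage" as distinct terms among the events that are always serious.

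On the comparison, Section 9.2.3 says that "rates of study AESIs observed among women enrolled in the pregnancy registry and their offsprings will be compared with available background event rates", in order to identify potential signals. Section 9.7.1 repeats this and allows background rates from public sources, the literature or the health databases. Neither section requires the background case definition to match Appendix 2.

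Section 9.5 expects spontaneous abortion at 1/7 (14.3%) without saying whether unexpelled losses are included. Section 9.3.1 adds that "the diagnoses will be based on clinician assessment as recorded in the medical record and/or databases", and Appendix 2 repeats that clause for each of the three rows above.

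**The concern.** A fetus found dead on ultrasound before 20 weeks and one expelled naturally at the same gestation are both natural early losses. Appendix 2 puts them in different rows. A background miscarriage rate from the literature or a database may count both. The registry numerator would then be narrower than the background numerator, and the comparison would be biased downwards.

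Spontaneous abortion is the most frequent outcome in the Section 9.5 planning table, so it is where a registry of at most about 214 pregnancies has the best chance of seeing an excess. The Pregnancy loss heading cannot serve as the combined outcome, because it also holds induced terminations and stillbirths. The earlier trial evidence in Section 7.1.3.2 was reported as one undivided figure ("10.3% of CYD-TDV exposed pregnancies resulted in the loss of the fetus, compared with 13.3% of placebo exposed pregnancies"), so an expelled-only rate may not be comparable with it.

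The second issue is an overlap. Death in utero is dated by the death and stillbirth by the delivery, so one fetus can meet both definitions.

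**Working it through.** **Inputs from the protocol.** Section 9.5: N = 214 at full participation, and spontaneous abortion expected at p0 = 1/7.

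**Reproducing the plan's figure.** 214/7 = 30.6, rounded to 31. 31/214 = 14.486%, with an exact (Clopper-Pearson) 95% CI of 10.06 to 19.93. This agrees with the table in Section 9.5.

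**Assumptions not in the documents.** (a) The background rate counts unexpelled losses. (b) A share s of natural losses before 20 weeks falls outside the spontaneous abortion row. The documents give no value for s, so a range is shown. (c) The planning figure of 14.3% stands in for the background rate.

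**Formula.** Rate shown in the row = p0 × RR × (1 − s), where RR is the true ratio of natural early loss to background.

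**A true 1.5-fold excess at N = 214.** 1.5 × 214/7 = 45.9, rounded to 46.

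| Share outside the row | Count in the row | Rate | Exact 95% CI |
|---|---|---|---|
| 0% (all natural losses) | 46 | 21.5% | 16.19 to 27.61 |
| 20% | 46 × 0.8 = 37 | 17.3% | 12.48 to 23.04 |
| 30% | 46 × 0.7 = 32 | 15.0% | 10.46 to 20.45 |
| 40% | 46 × 0.6 = 28 | 13.1% | not computed |

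With all natural losses counted, the interval excludes 14.3%. At 20% outside the row it no longer does. At 30% the count is 32, almost the 31 expected with no excess. The excess is fully masked when RR × (1 − s) = 1, that is s = 1 − 1/RR. For RR = 1.5 that is one third, so the row falls below 14.3% only if more than a third of losses lie outside it.

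**Chance of noticing.** The protocol states no numerical signal rule. Assume a signal is an exact 95% lower limit above 1/7, which needs at least 42 of 214. For a true 1.5-fold excess the probability is 76.4% with all natural losses counted, 19.0% at s = 20% and 4.0% at s = 30%. At 75% participation (N = 160) the three figures are 62.8%, 14.4% and 3.4%. At 50% (N = 107) they are 43.8%, 9.6% and 2.6%.

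**Overlap.** A fetus that dies at 18 weeks and is delivered at 21 weeks was dead and unexpelled before 20 weeks, so it is a death in utero. It was also delivered dead after 20 weeks, so it is a stillbirth. No precedence rule is given. Section 9.5 expects one stillbirth in 214 (0.467%). One such fetus counted as an additional stillbirth would make it 2/214 = 0.93%. This shows how sensitive a count of one is; it does not estimate how often the case arises.

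**The case against.** The strongest reply is that nothing is lost. Unexpelled deaths have their own row under the same heading, they are always serious events, and the comparison covers all outcomes of special interest. A careful reader can add the rows, and an analysis plan not shown here may do so. This stands: a reader might infer that missed abortions vanish from the study, and they do not. But the protocol fixes the outcomes to be compared, and none of them is natural early loss as a whole.

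Second, diagnoses follow the clinician's record. A missed abortion recorded as a miscarriage may be counted as one. It would therefore be too strong to say that the rate is lowered by construction. The clause may shrink the effect, but classification then depends on how each record is worded.

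Third, the 1/7 in Section 9.5 illustrates precision and is not the fixed comparator. A reader might infer that the registry will be tested against 14.3%, or that 14.3% includes unexpelled losses. The documents support neither. A background rate with the same expelled-only definition would produce no bias.

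Fourth, no passage supports any particular share outside the row. A reader might conclude that a real excess would appear below background. At 20% or 30% it would not; the row would still read above 14.3%.

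Fifth, unspecified abortion may include elective abortions. It is not simply a third label for natural loss, and keeping it apart is defensible.

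**Conclusion.** The point holds in limited form. The expulsion split, the absence of a combined natural early-loss outcome, the lack of a matching requirement on the background rate, and the overlap between death in utero and stillbirth all stand in the text. The understatement is conditional: it arises only if the background rate counts unexpelled losses, and its size depends on a share the documents do not give. If 20% to 40% of losses fall outside the row, a true rate of 21.5% would read as 17.3% to 13.1%. The overlap needs no assumption about the background, but its frequency is unknown. This is a possible downward bias in the most frequent planned outcome, worth removing because the remedy is cheap. It does not show that an excess will be hidden.

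**What to change.** In Appendix 2:

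- Keep the existing rows as they are.
- Add a combined outcome, natural pregnancy loss before 20 weeks: spontaneous abortion plus death in utero, however the uterus was emptied. Make this the outcome compared with background.
- Show it with and without unspecified abortions, as a sensitivity bound.
- Require the background rate to use the same definition.
- State one precedence rule so that each fetus is counted once, in death in utero or in stillbirth. Choose it to match the background stillbirth definition. Dating stillbirth by time of death without that check could create a new mismatch if the background rate is dated by delivery. The same rule settles whether such a fetus enters the combined outcome.

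The cost is a few lines in Appendix 2 and one derived variable, built from rows already collected. The drawback is that the bound including unspecified abortions may contain some elective ones, so it should not be the main figure.

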databases (secondary data sources). Study participation will require receipt of a signed informed consent form (ICF) or Assent form (AF) according to local regulations. CYD-TDV exposed pregnant women will be actively identified and recruited using pregnancy exposures reported to the national spontaneous adverse events following immunization reporting system (SI-PNI EAPV). As such, women included in the pregnancy registry will represent those receiving care in the public and private health care settings at the time of their pregnancy exposure. The start of follow-up for the pregnant women will be the date of first CYD-TDV vaccination during the exposed pregnancy and the date of birth for the offsprings. Study outcomes will include maternal, pregnancy, birth, neonatal and infant AESIs, as well as all other reported AEs. Study data will be collected by the study investigators (or research personnel designated by the investigators) through home visit and/or telephone interviews using a structured questionnaire. Self-reported information will be supplemented and confirmed through contact with the woman's physician or other health care provider (e.g., nurse), use of medical records (e.g., prenatal care booklet, hospital, primary health care unit or other settings where antenatal care was provided), and use of record linkages with existing databases (e.g., SINASC, SIM), subject to availability. In cases of discrepancies between data sources, the medical record will be used as the gold standard for most data, followed by databases. Women will be followed for 42 days after the end of pregnancy, irrespective of the duration of the pregnancy, and their offsprings will be followed for up to 12 months post-birth.

* Exact date will depend on timing of local and national EC approvals

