Participants' date of CYD-TDV immunization will be confirmed through probabilistic linkage (i.e., using nominal data) with the immunization registry; database linkages will be carried out by the DoH or study investigators depending on the availability of qualified personnel. When indicated, a women's self-reported exposure status will be reclassified using the immunization registry as the gold standard. In addition, reports of multiple CYD-TDV exposures during a pregnancy will be classified according to the earliest pregnancy exposure.

Women enrolled in the CYD-TDV pregnancy registry will be followed from the date of their first CYD-TDV vaccination during pregnancy (cohort entry) to up to 42 days following the end of the exposed pregnancy, regardless of the outcome of the pregnancy. The offspring of the exposed pregnancy will be followed for up to 12 months post-birth. In addition, women and offsprings enrolled prospectively (i.e., CYD-TDV exposure either soon before or after study start) will be followed until the earliest of: date of lost to follow-up, withdrawal of consent or death or end of study (July 2022).

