Maternal death	
 • Maternal death during pregnancy or ≤ 42 days of delivery; derived from maternal date of death and infant DOB

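### The maternal death endpoint is anchored on delivery and the infant's date of birth, so it does not classify deaths after a miscarriage, ectopic pregnancy or termination, although follow-up covers them

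*Protocol*

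**What the plan says.** The last row of Appendix 2 (pregnancy related adverse events of special interest) defines the endpoint as "Maternal death during pregnancy or ≤ 42 days of delivery" and says it is "derived from maternal date of death and infant DOB". No other source or rule appears in that row.

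The follow-up rules are wider. Section 9.1.1: "Women will be followed for 42 days after the end of pregnancy, irrespective of the duration of the pregnancy". Section 9.2.2 follows each woman from vaccination up to "42 days following the end of the exposed pregnancy, regardless of the outcome of the pregnancy".

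Appendix 2 also lists, as outcomes of interest, ways for a pregnancy to end without a birth:
- spontaneous abortion: "Fetal death with expulsion at <20 weeks of gestation";
- ectopic pregnancy: "Pregnancy with fertilized egg implanted and maturing outside the uterus";
- termination for fetal anomaly: "Abortion brought on intentionally when the embryo/fetus presents an abnormality";
- medically indicated abortion, abortion of unspecified type, and death in utero before 20 weeks.

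Section 9.7.1 uses all exposed pregnant women in the registry as the denominator for maternal outcomes, and compares observed rates with background rates. The Abstract and Section 9.4 name the national mortality database (SIM) as a source for supplementing and verifying maternal deaths.

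**The concern.** The derivation uses two dates, and one of them does not exist for a known part of the cohort. Two problems follow.

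First, the 42-day window starts at delivery, whereas follow-up starts its 42 days at the end of pregnancy. The study observes women after an early loss but has no rule that turns a death in that time into the endpoint.

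Second, the definition includes death during pregnancy, yet a woman who dies undelivered will in general have no infant date of birth. Her death meets the definition and fails the derivation.

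Both errors run the same way. Affected women stay in the denominator and their deaths do not reach the numerator, so a safety endpoint compared with background mortality can only be under-counted.

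**Working it through.** **Step 1. Compare the rules by how the pregnancy ended.**

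| How the pregnancy ended | Followed for 42 days afterwards (9.1.1, 9.2.2) | Within the Appendix 2 definition | Derivable from date of death and infant date of birth |
|---|---|---|---|
| Live birth | yes | yes | yes |
| Miscarriage, ectopic pregnancy, termination | yes | no delivery from which to count | no |
| Woman dies undelivered | followed until death | yes (during pregnancy) | in general no |

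Stillbirth is left out. There is a delivery, but the protocol does not say whether its date is held as an infant date of birth.

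**Step 2. Look for another rule.** Most other rows of Appendix 2 rest wholly or partly on clinician assessment in the medical record or databases. The maternal death row does not. SIM can supply the date of death, but not the date from which the 42 days run. Section 9.3.2 lists last menstrual period and estimated date of delivery, and no date of pregnancy end. No other section gives a second derivation.

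**Step 3. Reproduce the protocol's figure.** Section 9.5 gives 31 of 214 = 14.486%, 95% CI 10.06 to 19.93, for miscarriage. The exact (Clopper-Pearson) interval for 31/214 is 10.06 to 19.93, which agrees. The rows for 23/160 (9.34 to 20.78) and 15/107 (8.06 to 22.07) also agree.

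**Step 4. Size the group with no infant date of birth, from miscarriage alone.** Expected count = N × 1/7:
- 100% participation: 214/7 = 30.6, about 31;
- 75%: 160/7 = 22.9, about 23;
- 50%: 107/7 = 15.3, about 15.

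Ectopic pregnancies and terminations would add to these, but the protocol gives no rate for them.

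**Step 5. Illustrate the effect on the estimate.** Suppose no maternal death is classified. The upper exact 95% limit for 0 of n is 1 − 0.025^(1/n). The registry would report it on all women, while the post-pregnancy window can classify only those without a miscarriage:
- 0/214: 1.71%; 0/(214 − 31) = 0/183: 2.00%;
- 0/160: 2.28%; 0/(160 − 23) = 0/137: 2.66%;
- 0/107: 3.39%; 0/(107 − 15) = 0/92: 3.93%.

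The limit is too low by about 0.3 to 0.5 percentage points. This covers the post-pregnancy window only and ignores other non-birth endings.

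**The case against.** A reader might infer that these deaths would go undetected. The documents do not support that. Section 9.3.1 makes all serious and non-serious events primary endpoints, including other reported events in pregnancy and the puerperium. Section 11.1.1 lists maternal death as always serious, and SIM holds dates and causes of death. Such a death may well be recorded; what it would lack is classification as this endpoint.

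A reader might also infer that every death in pregnancy is excluded. It is not: the definition names death during pregnancy, and the clause about dates can be read as describing only the post-delivery part. That reading is sensible, but the text does not state it, and it leaves deaths after a non-birth ending unresolved.

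Nor is 31 of 214 a lower bound or a number of deaths. It is an expected count of miscarriages at full participation, with an interval of 10.06% to 19.93%, or about 22 to 43 women. The protocol gives no maternal mortality rate, so no number of missed deaths can be derived.

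It is fair to say that a follow-up period may be longer than an endpoint window without contradiction. Here, though, the protocol extends follow-up after early losses on purpose and gives no reason for leaving that time out of the endpoint.

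The strongest point concerns practical effect. Inclusion requires signed consent, enrollment starts in July/August 2019 after the 2016 to 2018 campaigns, and Section 9.9 says that most outcomes are retrospective and that women may have died before enrollment. Few participants could contribute a maternal death under any rule. This stands, and it limits the size of the problem. It does not make the rule correct.

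**Conclusion.** The stated rule is wrong as written, with a probably small numerical effect. It does not classify a death within 42 days of a miscarriage, ectopic pregnancy or termination as the maternal death endpoint, and its derivation does not deliver the part of the definition on death while undelivered. The error can only lower the count. This is not a detail left for the statistical analysis plan, because the protocol states a derivation and states it too narrowly.

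About 14% of the cohort (31 of 214, 23 of 160 or 15 of 107 women) falls outside the post-pregnancy part of the rule through miscarriage alone. This assumes that the protocol's 1/7 rate applies to this registry. Women with a known miscarriage remain in the denominator whether maternal death is treated as a maternal outcome (all women) or as a pregnancy outcome (pregnancies with known outcome). No sample size or precision figure in the protocol changes.

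**What to change.** Replace the maternal death row in Appendix 2 with: death during pregnancy or within 42 days after the end of pregnancy by any outcome, derived from the date of death and the date the pregnancy ended (delivery, loss or termination); a death before the pregnancy ended counts as during pregnancy.

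This brings the endpoint into line with Sections 9.1.1 and 9.2.2. The cost is one line in the appendix. The date the pregnancy ended is already needed to run the 42-day follow-up, but Section 9.3.2 does not list it, so it should be added there and its presence in the case report form confirmed.
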